### **3.2.8.3. Skin: Early-Phase (0–60 min) and Late-Phase (6 hr) Skin Reaction to Allergen Challenge**

The SPT with serial allergen titration assesses the early phase reaction (EPR) at 0-60 min. The intradermal allergen injection will be performed to assess late phase reaction (LPR) at 6 hours. The early phase reaction is characterized by histamine release and is thought to reflect cutaneous mast cell degranulation upon allergen exposure. The allergen-induced cutaneous LPR is characterized by an influx of inflammatory cells, including basophils, eosinophils, activated CD4+-cells, and neutrophils which arrive at the site of inflammation some hours after provocation.

Allergen specific immunotherapy with Timothy Grass has been shown to decrease both the early phase reaction after SPT, and late phase reaction after intra-dermal allergen challenge, as measured by the decrease of wheal size post challenge (Scadding, 2015b). In addition, short term grass SCIT treatment (13 weeks) led to significant and lasting reduction of LPR with statistical significance 12 months after the end of SCIT (Chaker, 2015a) (Chaker, 2015b). We hypothesize that dupilumab as an adjunct to SCIT treatment may further reduce skin allergic response to Timothy Grass and can further decrease LPR compared to SCIT alone. Based on expected reduction of IgE levels 12 weeks after dupilumab treatment in past AD studies, a reduction in mast cell activation may result in reduction in EPR and therefore reduced wheal sizes may also be expected.

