## **5.7. Analyses of Efficacy Variables**

For all efficacy variables, unless specified, the analysis will be comparisons of

- dupilumab + SCIT versus SCIT
- dupilumab versus placebo
- dupilumab + SCIT versus dupilumab for percent change and change in TNSS AUC only

The efficacy analyses will be based on the FAS Population. All statistical tests will be 2-sided at the 5% significance level. All confidence intervals (CIs) will be 2-sided 95% CIs.

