### **5.7.1. Analysis of Primary Efficacy Variable**

The primary endpoint will be analyzed by using the analysis of covariance (ANCOVA) model as the primary analysis method. The model will include treatment group being the main factor and baseline value as the covariate. The missing AUC value at a visit directly when a patient does not have any TNSS score collected at the visit, will be imputed by multiple imputation (MI) methods 40 times to generate 40 complete data sets by using the Statistical Analysis System (SAS) procedure MI following the 2 steps below:

Step 1: The monotone missing pattern is induced by Markov Chain Monte Carlo (MCMC) method in MI procedure using seed number 16115. The monotone missing pattern means that if a patient has missing value for a variable at a visit, then the values at all subsequent visits for the same variable are all missing for the patient.

Step 2: The missing data at subsequent visits will be imputed using the regression method for the monotone pattern with seed number 51161 and adjustment for covariates including treatment groups and relevant baseline.

Each of the 40 complete datasets will be analyzed using an ANCOVA model with treatment group being the main factor and baseline value as the covariate. The SAS MIANALYZE procedure will then be used to generate valid statistical inferences by combining results from the 40 analyses using Rubin's formula. The least-squares (LS) mean for each treatment group with its corresponding standard error (SE), the LS mean difference between treatment group and its corresponding SE and 95% CI, and the p-value corresponding to the between-treatment-group difference will be reported.

In case of missing TNSS scores at one or more time points at a visit, all available TNSS scores collected at the visit will be used to calculate the AUC at the visit. The missing TNSS score at timepoints will not be imputed. The algorithm for calculation of AUC is provided in Section [6.2](#).

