## **5.12. Analysis of Biomarker Data**

All biomarker analyses will be performed on the FAS using all observed data. Descriptive statistics for the observed values, change from baseline and percent change from baseline values by treatment and visit will be provided for the biomarker variables.

The Wilcoxon signed-rank test will be used to test if the change or percentage change from baseline value is significantly different from zero. P-value will be reported.

Exploratory analyses for the difference between dupilumab groups and placebo on the change from baseline and percent change from baseline values will be performed using a rank-based ANCOVA model with treatment group and the relevant baseline values as covariate. Missing value will be imputed by LOCF method for visits between post-baseline to week 17. After week 17, no imputation will be made. P-value for difference between dupilumab +SCIT and SCIT will be provided.

Correlation of baseline serum Timothy Grass sIgE, Timothy Grass specific IgG, sIgG4, TARC and total IgE, absolute change or percent change at weeks 4, 8, and 17 from baseline in these biomarkers; with the following clinical endpoints will be explored using the Spearman's rho test. Both Spearman correlation coefficients and p-value will be reported. Correlation of baseline serum Timothy Grass sIgE, Timothy Grass specific IgG, sIgG4, TARC and total IgE with the following clinical endpoints will also be analyzed by the ANCOVA model with the clinical endpoint as the dependent variable and the baseline biomarker as the covariate, treatment group, and treatment group by baseline biomarker interaction as the factors. The missing values will be imputed using post-baseline LOCF. Similar correlation analysis will be performed for the subclasses of Timothy Grass sIgG other than sIgG4 pending on available data.

- Change and percent change from baseline in TNSS AUC post NAC over the first hour after the challenge (0-1 hr post peak TNSS) at week 17
- Change and percent change from baseline in TOSS AUC post NAC over the first hour after the challenge (0-1 hr post peak TNSS) at week 17
- Change and percent change from baseline (last pretreatment measurement) to week 17 in Skin Prick Test with Serial Allergen Titration, as measured by AUC of the average wheal sizes (diameter) after the challenge (early phase reaction)

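### The exploratory baseline-biomarker ANCOVA in SAP 5.12 leaves out the clinical endpoint's own baseline, so its main effect cannot separate prediction of the week-17 outcome from tracking of baseline severity

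*SAP*

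**What the plan says.** SAP 5.12 (Analysis of Biomarker Data) explores how baseline sIgE, sIgG, sIgG4, TARC and total IgE relate to clinical endpoints. One tool is Spearman correlation with p-values. The other is an "ANCOVA model with the clinical endpoint as the dependent variable and the baseline biomarker as the covariate, treatment group". The only further term in that model is the product of marker and arm. The listed outcomes begin with "Change and percent change from baseline in TNSS AUC post NAC over the first hour after the challenge" and continue with the same two scales for TOSS AUC, skin-prick AUC and the 6-hour intradermal wheal. Five markers and eight outcomes make 5 × 8 = 40 pairs.

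The endpoint's own baseline is not among the terms. Elsewhere the SAP includes the relevant baseline. For the primary endpoint, "The model will include treatment group being the main factor and baseline value as the covariate" (SAP 5.7.1). For the between-group biomarker comparison in the same section, the plan is a "rank-based ANCOVA model with treatment group and the relevant baseline values as covariate". SAP 5.7.2 does likewise. No reason is given for the exception.

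For efficacy, "All statistical tests will be 2-sided at the 5% significance level" (SAP 5.7), and 5.12 sets no other level. SAP 5.7.3 states that multiplicity is not controlled. SAP 5.12 does not say whether the main effect or the interaction is the test of interest.

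**The concern.** Change is week 17 minus baseline, so the outcome carries the baseline score with a negative sign. A marker that correlates with the baseline score can then correlate with change through regression to the mean, while saying nothing about week 17 that the baseline score did not already say. Percent change can inherit the same problem.

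A link between marker and severity is plausible but not documented. Protocol 3.2.8.3 connects IgE with mast-cell activation and wheal size. Enrolment requires a peak TNSS of at least 7 at the challenge that supplies the baseline (Protocol 6.2.1), which makes some regression to the mean likely.

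At stake is what the trial reports about which baseline markers go with response. A significant main effect could be read as prediction when it only reflects severity at entry.

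**Working it through.** **The plan's own figure.** The only computed design figure is the primary power. Noncentrality = 29 / (35 × √(2/25)) = 29 / 9.90 = 2.93. With 48 df and 2-sided 0.05, power is 81.9% against the stated 80%, so it reproduces. It does not bear on SAP 5.12, for which no error rate is given beyond the nominal 5%.

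**Inputs.** From the documents: four arms of 25, 2-sided 0.05, and model terms arm, marker and arm × marker (8 parameters, 92 residual df). Assumed, because the documents do not give them: r, the correlation of marker with baseline score, and ρ, the correlation of baseline with week-17 score. Data are taken as complete; the SAP would use post-baseline LOCF.

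**Case A: marker linked to week 17 only through the measured baseline, additive arm effects, absolute change.** With equal variances at the two challenges,

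corr(change, baseline) = −√((1 − ρ)/2), so corr(change, marker) = c = −r√((1 − ρ)/2).

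For r = 0.3 and ρ = 0.5, |c| = 0.3 × 0.5 = 0.15. The noncentrality is about 0.15 × √92 / √(1 − 0.0225) = 1.46, and a 5% test on 92 df then rejects in 30% of trials. Simulation of the planned model (4,000 runs per cell) gives:

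| r | ρ = 0.3 | ρ = 0.5 | ρ = 0.7 |
|---|---|---|---|
| 0 | 5% | 5% | 5% |
| 0.2 | 20% | 16% | 12% |
| 0.3 | 40% | 30% | 19% |
| 0.5 | 82% | 69% | 47% |

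The formula agrees with every non-null cell to within 2 points. With only the two SCIT arms (n = 50), the ranges are 12–22% at r = 0.3 and 26–53% at r = 0.5. Spearman pooled over arms with no treatment effect, at ρ = 0.5, gives 16%, 30% and 67% for r = 0.2, 0.3 and 0.5. Adding the endpoint's baseline to the ANCOVA returns the main effect to 4.5–5.8% in every cell.

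**Interaction, Case A.** It rejects in 4.3–5.8% of trials, so there is no inflation. The cost is precision. Given baseline, the residual variance is proportional to 1 − ρ²; for the raw change it is proportional to 2(1 − ρ). The ratio is (1 + ρ)/2, or 0.65, 0.75 and 0.85 at ρ = 0.3, 0.5 and 0.7. In one simulated setting, adding the baseline raised power for the interaction from about 66% to 77–79%.

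**Case B: proportional arm effects** (−55% and −26% from the sample-size section; other arms, baseline mean 6.5 and SD 1–2 assumed; r = 0.3–0.5). For percent change the main effect rejects in 5–6% when week 17 is proportional to baseline, and in anything from about 6% to 59% when there is also regression to the mean. The interaction rejects in 4–9%, and in about 15% for percent change at r = 0.7. Adding baseline as a main effect does not cure that (up to 16%).

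**Case C: marker tracks a stable severity T seen at both challenges, additive effects.** Baseline = T + e₁ and week 17 = T + shift + e₂, so change = shift + e₂ − e₁. T cancels, and the planned main effect on absolute change rejects in 4.6–5.4%. The adjusted main effect rejects in 13.5–88%, because measured baseline is a noisy stand-in for T and the marker adds real information about week 17.

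**The case against.** The strongest reply is Case C. A serum marker may well reflect stable sensitisation rather than one day's score. On absolute change with additive effects the planned model is then right, and it is the adjusted main effect that exceeds 5%. Choosing between change and baseline-adjusted outcome is choosing a question. This stands, and it is why adjustment alone is not a sufficient remedy.

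Second, prediction of treatment response is the interaction, which SAP 5.12 already includes and which is not inflated under additive effects. This stands too, but the SAP does not name it as the test, so the main effect remains open to the same reading.

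Third, a reader might infer from Protocol 3.2.8.3 that a baseline marker–severity correlation is expected. The text does not go that far: "Based on expected reduction of IgE levels 12 weeks after dupilumab treatment in past AD studies, a reduction in mast cell activation may result" concerns IgE reduction on treatment and gives no baseline correlation. For TNSS, each subject is titrated to a score of at least 7 and that concentration is reused at week 17 (Protocol 5.2 and 8.2.1.1), which could weaken any such link. The fixed-concentration skin tests have no such feature.

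Fourth, a reader might infer that severity markers will be declared predictors of response far more often than 5%. The SAP has no rule for declaring a predictor, calls the correlations exploratory, and claims no multiplicity control. The inflation also depends on correlations that the documents do not give.

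**Conclusion.** The omission is real, out of line with the SAP's other ANCOVAs, and cheap to repair. The main effect and the baseline-marker Spearman correlation with change cannot tell prognostic information beyond baseline from tracking of baseline severity.

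The 12–82% range holds only if the marker reaches week 17 solely through the measured baseline, for absolute change, with r = 0.2–0.5 and ρ = 0.3–0.7. The rate is about 5% if the marker is unrelated to baseline severity, or in Case C. It is 5–6% for percent change, the primary endpoint's scale, when week 17 is proportional to baseline. The documents do not show which structure applies, so an unconditional statement of inflation is not supported.

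The interaction keeps its size under additive effects but is less precise than it could be, and proportional arm effects can inflate it. Only exploratory conclusions are affected.

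**What to change.** In SAP 5.12:

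- Add the endpoint's own baseline as a covariate in the baseline-biomarker ANCOVA, for example baseline TNSS AUC when the outcome is change or percent change in TNSS AUC.
- Add a baseline-by-treatment term as a check on the interaction, since arm effects may be proportional.
- Name the treatment-by-biomarker interaction as the test of predicting treatment response. Describe a main effect as prognostic association only, because even the adjusted one can exceed 5% when the marker tracks latent severity.
- Use partial rank correlation given the baseline clinical value for the baseline-marker Spearman analyses.
- Report the unadjusted version alongside.

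The cost is one degree of freedom for the covariate, or four with the baseline-by-treatment term (1 + 3), out of 92, plus a second exploratory table. No new data are needed: SAP 4.1 already lists the baseline of each of these endpoints for derivation.

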## 6. DATA CONVENTIONS

The following analysis conventions will be used in the statistical analysis.

### 6.1. Definition of Baseline for Efficacy/Safety Variables

Unless otherwise specified, the baseline assessment of the study for all measurements will be the latest available valid measurement taken prior to the first administration of study drug. If any randomized patients are not treated, the baseline will be the last value on or prior to the randomization. The baseline of TNSS is defined in Section 4.5.1.

The following rules specify the determination of baseline by both date/time information:

- For the AE, lab, PK and ADA data, both date and time of the measurement will be used to determine baseline by comparing with the first injection date and time.
- For other data except AE, lab, PK or ADA, only date of the measurement will be used to determine baseline by comparing with the first injection date.

For the rescreened patients, all data from the same patient will be used to derive baseline regardless if the data is from the screen-failure subject ID or enrolled subject ID.

### 6.2. Data Handling Convention for Efficacy Variables

#### Algorithm for calculation of area under curve (AUC)

The AUC will be calculated using trapezoid rule. For example, the AUC within 1 hour will be calculated using formula

$$AUC_{[0-1h]} = [\sum_{i=1}^5 (t_i - t_{i-1}) * (D_i + D_{i-1})/2]/(t_5 - t_0)$$

Where

- $D_i$  is the TNSS value obtained at time  $t_i$
- $t_i$  is the time (in hours) for which  $D_i$  is measured, such as  $t_0 = 0$ ;  $t_1 = 1/12$  hour for 5 minutes,  $t_2 = 0.25$  hour for 15 minutes,  $t_3 = 0.5$  hour for 30 minutes,  $t_4 = 0.75$  hour for 45 minutes and  $t_5 = 1$  for 1 hour.

In case of missing TNSS scores at one or more time points at a visit, all available TNSS scores collected at the visit will be used to calculate the AUC at the visit. The missing TNSS score at timepoints will not be imputed.

For example, if there is one missing timepoint value within 1 hour, then the AUC within 1 hour at the visit will be calculated using the 5 available TNSS scores. These 5 scores will be numbered as  $D_0, D_1, D_2, D_3, D_4$ , at timepoints  $t_0, t_1, t_2, t_3, t_4$ , the AUC will be calculated as

$$AUC_{[0-1h]} = [\sum_{i=1}^4 (t_i - t_{i-1}) * (D_i + D_{i-1})/2]/(t_4 - t_0)$$

#### Data Handling Convention for Missing Data

Rules for handling missing data for primary and secondary efficacy variables are described in Section [5.7.1](#) and Section [5.7.2](#).

### **Adverse event**

If the intensity of a TEAE is missing, it will be classified as “severe” in the frequency tables by intensity of TEAE. If the assessment of relationship of a TEAE to the investigational product is missing, it will be classified as “related” in the frequency tables by relation to the investigational product.

#### Adverse event start date

AE start date will be used for AE classification and analysis of AESIs. If AE start date is not complete, then the character variable will keep the original incomplete date, the numerical date variable will be imputed and an imputation flag will indicate which date component is missing.

If AE start day is missing, and AE start month and year are not missing: If AE start year is the same as first dose year and the AE start month is the same as the first dose month) then impute AE start day using the day of first dose. If this leads to a date after the AE end date, use AE end date instead. Otherwise impute the AE start day using the first day of the month. If this leads to a date before informed consent, the informed consent date will be used. Imputation flag is ‘D’.

If AE start month is missing, and AE start year is not missing: If AE start year is less than the first dose year, use the informed consent day and month. If AE start year is equal to the first dose year, use the first dose day and month. If this leads to a date after the AE end date, use AE end date instead. If AE start year is after the first dose year, use 01 January. Imputation flag is ‘M’.

If AE start year is missing: Impute AE start date using the day of first dose. If this leads to a date after the AE end date, use AE end date instead. Imputation flag is ‘Y’.

#### Adverse event end date

The general recommendation is not to impute AE end date. However, since AE end date will be used for AE starting date imputation, In order to carry through the logic for programming, the following intermediate step will be used. Afterwards, only the original character/numeric date recorded in CRF will be kept in the final analysis dataset.

If AE end day is missing, and AE end month and year are not missing: Impute AE end date using the last day of the month. If this leads to a date after end of study follow up date, use end of follow up date instead.

If AE end month is missing, and AE end year is not missing: Impute AE end date using 31 December as the day and month. If this leads to a date after end of study follow up date, use the end of follow up date instead.

If AE end year is missing: Impute AE end date using the end of follow up date.

### **Medication start and end date missing**

To determine whether a medication is prior medication or concomitant medication or both, the missing medication start date is estimated as early as possible, and the missing medication end date is estimated as late as possible. If the medication start date is missing, the onset day will not be calculated in medication listings.

Prior medication start date

If start day is missing, and start month and year are not missing: Impute the start day using the first day of the month. Imputation flag is 'D';

If start month is missing, and start year is not missing: Impute the day and month using 01 January. Imputation flag is 'M'.

If start year is missing: Impute start date using 2 years before inform consent date. Imputation flag is 'Y'.

A special note: for start date with year missing, the general principle is not to impute. However in order to simplify the programming flow, the imputation is proposed to in line with the protocol which specifies to collect up to 2 years prior medication. Since the start date of prior medication will not be used in any analysis, the rule will not impact the analysis result.

Prior medication end date

If end day is missing, and end month and year are not missing: Impute end date using the last day of the month. If this leads to a date on or after first dose intake date, use first dose intake date -1 instead. Imputation flag is 'D'.

If end month is missing, and end year is not missing: Impute end date using 31 December as the day and month. If this leads to a date on or after first dose intake date, use first dose intake date -1 instead. Imputation flag is 'M'.

If end year is missing: Impute end date using the first dose intake date -1. Imputation flag is 'Y'.

Concomitant medication start date

The imputation rule for concomitant medication start date is the same as AE start date.

Concomitant medication end date

If end day is missing, and end month and year are not missing: Impute end date using the last day of the month. If this leads to a date after end of study follow up date, use end of follow up date instead. Imputation flag is 'D'.

If end month is missing, and end year is not missing: Impute end date using 31 December as the day and month. If this leads to a date after end of study follow up date, use the end of follow up date instead. Imputation flag is 'M'.

If end year is missing: Impute date using the end of follow up date. Imputation flag is 'Y'.

Medication coding

Medications whose ATC level 4 cannot be coded will be summarized by setting ATC4=ATC2 in the table programs. However, these uncoded ATC level 4 records still need to be confirmed with study DM and study MD.

PCSV

Patients who had post-baseline PCSV but missing baseline value will be regarded as having treatment emergent PCSV.

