### 5.3. Prior/Concomitant Medications/Procedures

Number and proportion of patients taking prior/concomitant medications, prohibited medications and rescue medications will be summarized, sorted by decreasing frequency of ATC Level 2 and ATC level 4, based on the overall incidence for the combined treatment groups. Patients will be counted only once for each medication class (ATC level 2 and 4) linked to the medication.

Number and proportion of patients taking prior/concomitant procedures will be summarized, sorted by decreasing frequency of SOC and PT based on the overall incidence for the combined treatment groups. Patients will be counted only once for each SOC and PT linked to the procedure.

Concomitant medications used to treat SCIT related adverse events will be tabulated separately.

Prior medications or procedures started before screening visit and started between screening visit and first injection date will be summarized separately.

Listing of medications and procedures will be provided.

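### SAP 6.2 classifies drugs by their latest possible end date, but its prior-medication rule cuts that date to the day before first dose, and nothing says which governs

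*SAP*

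**What the plan says.** SAP 6.2, under the heading on missing medication dates, gives the purpose of the imputation, "To determine whether a medication is prior medication or concomitant medication or both", and the principle: "the missing medication start date is estimated as early as possible, and the missing medication end date is estimated as late as possible". It then gives four sets of rules, headed by class.

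- **Prior start:** first of the month, or 1 January. A missing year becomes two years before consent.
- **Prior end:** last day of the month, or 31 December, with this limit: "If this leads to a date on or after first dose intake date, use first dose intake date -1 instead". For a missing year: "If end year is missing: Impute end date using the first dose intake date -1".
- **Concomitant start:** "The imputation rule for concomitant medication start date is the same as AE start date". That rule gives the first-dose date when the partial date shares the first-dose month, or shares its year with the month missing. For a missing year: "If AE start year is missing: Impute AE start date using the day of first dose".
- **Concomitant end:** last day of the month, 31 December, or end of follow-up, never later than end of follow-up.

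A note on missing prior start years adds: "Since the start date of prior medication will not be used in any analysis, the rule will not impact the analysis result". SAP 5.3 says: "Prior medications or procedures started before screening visit and started between screening visit and first injection date will be summarized separately".

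Two protocol sections bear on this. Section 7.7 counts as concomitant any drug begun before the study and still in use during it. Section 10.5 assumes that an incomplete AE or concomitant-medication start falls on or after first intake, unless the partial date clearly shows otherwise.

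**The concern.** Two of the four rule sets follow the stated principle (prior start, concomitant end). The prior end rule does not: it overrides the latest possible end in exactly those records where that end would make the drug concomitant as well.

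The layout is also circular. The programmer must know the class to choose the heading, but the dates produced under the heading are supposed to give the class. Two programmers working in good faith could produce different tables.

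At stake are the prior, concomitant, prohibited and rescue medication counts described in SAP 5.3. A drug of a prohibited class that may have been in use after randomisation could disappear from the prohibited table because its stop date was incomplete.

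**Working it through.** The plan gives no figure to reproduce. The check applies each rule to the same record.

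**Assumed dates, for illustration only:** consent 20 Aug 2018, first dose (day 1) 15 Oct 2018, end of follow-up on day 169. Day 169 is 15 Oct 2018 + 168 days = 1 Apr 2019.

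**Partial end date, start known and before day 1:**

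| Recorded end | Prior heading | Class | Concomitant heading | Class |
|---|---|---|---|---|
| Oct 2018 | 14 Oct 2018 | prior only | 31 Oct 2018 | both |
| 2018 | 14 Oct 2018 | prior only | 31 Dec 2018 | both |
| year missing | 14 Oct 2018 | prior only | 1 Apr 2019 | both |

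The concomitant heading gives the latest possible date in each row, so it matches the stated principle. The prior heading does not.

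**Partial start date (no earlier recorded end):**

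| Recorded start | Concomitant heading | Earliest possible |
|---|---|---|
| Oct 2018 | 15 Oct 2018 | 1 Oct 2018 |
| 2018 | 15 Oct 2018 | 1 Jan 2018 |
| year missing | 15 Oct 2018 | 20 Aug 2016 |

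Used for classification, the concomitant start rule would never call these drugs prior. In the first row, 14 of the 31 possible start days precede day 1.

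**Share of possible stop days on or after day 1, only the day missing.** With first dose on day f of an m-day month, the share is (m − f + 1)/m.

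- f = 10, m = 30: (30 − 10 + 1)/30 = 21/30 = 70%. The other 9/30 = 30% are true stops before day 1.
- f = 15, m = 31: (31 − 15 + 1)/31 = 17/31 = 55%.
- Averaged over all first-dose days with m = 30: (m + 1)/(2m) = 31/60 = 52%.

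These shares assume that every stop day in the month is equally likely. Under the prior heading all such records are counted as prior only.

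**Use of the prior start date.** SAP 5.3 separates prior drugs begun before screening from those begun between screening and first injection. That split needs a start date. Setting a missing start year to two years before consent always puts the drug in the before-screening group. The rule therefore does affect an output.

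**The case against.** The best defence is a two-step reading: classify by the earliest/latest principle, then use the headed rules only to fill in dates. Protocol 7.7 could also be read as fixing the class when the drug is recorded. Either would avoid the miscount, but the SAP states neither and says that the imputation is what determines the class. Under the two-step reading the day and month cap would act only on drugs already classed as also concomitant, so it would still contradict the classification.

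Several stronger readings are tempting, and the documents do not support them.

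- *The cap touches only drugs that really spanned day 1.* It does not. A drug stopped on the 5th, recorded by month only, with first dose on the 10th, is also capped, and correctly so. These are the 9 in 30 above.
- *The medication counts are wrong, and a missing end year always means prior only.* That holds only if the prior heading decides the class. The concomitant heading gives end of follow-up.
- *The borrowed AE start rule is an error.* It follows Protocol 10.5. It conflicts with the SAP's own principle only if it is used to decide whether a drug is also prior.
- *Imputed dates distort the rescue-treatment adjudication.* SAP 4.4 lists timing among the things considered, but nothing says that imputed dates are used.

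The uniform stop-day assumption is also open to challenge. Concomitant medications are recorded at every visit, weekly to week 8, so a drug continuing past day 1 would usually be asked about soon afterwards.

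**Conclusion.** The point holds as an internal contradiction and an unresolved ambiguity. The prior end-date rule cannot be reconciled with the latest-possible-end principle, and the SAP does not say which heading governs a drug with a pre-dose start and a partial end. If the prior heading governs, drugs possibly in use after day 1 drop out of the descriptive concomitant and prohibited tables, contrary to Protocol 7.7. The sentence denying any analytic use of prior start dates is incorrect on any reading.

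The importance is minor. The number of partial dates is not given and may be small. The 70% and 52% figures are illustrations under equally likely stop days, not estimates of misclassified records. The primary analysis, an ANCOVA of TNSS AUC on all randomised subjects, does not use these dates.

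**What to change.** In SAP 6.2:

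1. State that classification comes first, from the earliest possible start and latest possible end, with a missing end year taken as end of follow-up. A drug is prior if its earliest start precedes first dose, concomitant if its latest end is on or after first dose, and both if both hold.
2. Delete the limits that set a prior end date to the day before first dose, or say that they may not be used for classification.
3. Keep the concomitant start rule, if wanted, for imputed onset dates only, and say that it does not decide whether a drug is also prior. If the rule itself is changed, list the departure from Protocol 10.5 in SAP 1.2.4.
4. Delete the sentence saying that the prior start date enters no analysis, since SAP 5.3 uses it.

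The cost is a few lines of SAP text and a small programming change before database lock. The price in the tables is over-inclusion: some drugs that truly stopped before day 1 will be counted as both (9 of 30 possible stop days in the example), as will some that truly started on or after it (31 − 14 = 17 of 31 possible start days with first dose on 15 October). That errs in the direction the SAP's own principle already chose.
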